## **5 RANDOMIZATION, BLINDING AND SUBJECT IDENTIFICATION PROCEDURES**

### **5.1 Randomization**

Subjects will be prospectively randomized into the FILM Clinical Trial. Randomization will occur on the day of surgery. Prior to surgery, the subject will have provided written informed consent, completed all baseline procedures and met the requirements of inclusion and exclusion criteria. Randomization should be performed as closely as possible to the mapping procedure to minimize the incidence of dropout.

Subjects will be randomly assigned on a one to one (1:1) basis to either the B-P Arm (LN mapping with Blue dye followed by LN mapping with PINPOINT) or the P-B Arm (LN mapping with PINPOINT followed by LN mapping with Blue dye). Randomization will be stratified by study site. Permuted block randomization will be performed within strata. To minimize the opportunity for the sequence to be predicted, the block size will be variable and randomly chosen from small multiples of 2 (i.e. 2, 4 or 6). The randomization schedules will be generated in advance using a computerized random number generator. Investigational sites will not have access to the randomization schedules.

Randomization will be accomplished using a secure web-based software (REDCap) supported by the Data Coordinating Center. Treatment assignment is made only after verification of proper informed consent execution and study eligibility.

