#### 10.4 Sample Size Considerations

The clinical literature provides an estimate of the expected effectiveness of LN mapping with ICG and Blue Dye. 12 studies using ICG for the purposes of LN mapping have been published (Table 1). Detection rates for LN mapping with ICG and Blue dye are reported to occur in a wide range (33-100% for ICG and 40-80% for Blue dye). A number of factors play a role in the identification of LN including tumor size, familiarity with LN mapping technique (learning curve) and obesity.

A weighted average of published LN detection rates for Blue dye and ICG (i.e., PINPOINT) in gynecological cancer suggests unilateral detection rates of 91% for ICG and 80% for Blue dye. However, we assumed LN detection rates in gynecological cancer of 84% and 80% using ICG and Blue dye, respectively. We used a lower LN detection rate of 84% for ICG and a LN detection rate at the upper end of the range for Blue dye as a conservative approach to the sample size calculation. We also assumed a non-inferiority margin of 5%.

The power calculation was performed for a 2-level hierarchical model in which nodes are nested within subject. Power was calculated as a function of the effective sample size (ESS), which is a function of the total number of nodes excised, the number of nodes within subjects (clusters), and the intra-cluster correlation (ICC). Specifically,  $ESS = n / VIF$ , where  $n$  is the total number of nodes excised across all patients, and VIF is the variance inflation factor, calculated as

$VIF = 1 + (m - 1) \times ICC$ , where  $m$  is the number of nodes per subject. Because we expect to excise 3 to 4 nodes per subject, with 150 subjects we expect to excise  $3.5 \times 150 = 525$  nodes. With 3.5 nodes per subject on average and an ICC at most 0.125 we will have VIF at most  $1 + (2 \times 3.5 - 1) \times 0.125 = 1.75$  and an ESS at least  $525 / 1.75 = 300$  nodes. Note that here  $m$  is twice the number of expected nodes per subject, since nodes will be identified using 2 different methods within the same subject. We expect the ICC to be at most 0.125 based on our estimate of the ICC = 0.07 from Crane et al..

With an ESS of at least 300 Ns we will have at least 82% power to reject  $H_{01}$  above and claim non-inferiority of PINPOINT with respect to Blue dye. This sample size calculation was

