performed using nQuery Advisor ® 7.0 (Copyright © 1995-2007, Statistical Solutions, Saugus, MA). We will test the hypothesis using a two-sided 95% confidence interval (i.e., two-sided significance level of 0.05). We will enroll subjects and identify Ns using both Blue dye and PINPOINT as described above in section 8.3.1.5 until we have at least 525 LNs identified, regardless of the method used to identify them. We expect that we will enroll approximately 150 subjects to obtain 525 nodes (based on clinical literature suggesting an average of 3-4 Ns excised per subject).

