- overall percent agreement = $100\% \times (A + D) / (A + B + C + D)$
- positive percent agreement = $100\% \times A / (A + C)$
- negative percent agreement = $100\% \times D / (B + D)$

As sensitivity analyses, we will perform the non-inferiority tests of these secondary outcomes using the mITT analysis set. We will also perform sensitivity analyses of these secondary endpoints using a best-case and a worst-case scenario. The best-case scenario will consider nodes with missing histology to be lymphoid tissue for PINPOINT and non-lymphoid tissue for Blue dye. The worst case scenario will consider nodes with missing histology to be non-lymphoid tissue for PINPOINT and lymphoid tissue for Blue dye.

The last secondary objective of the study is to find the anatomic distribution of lymph nodes. Table 8 summarizes the data to address this secondary objective. We will use Fisher's exact test to compare study arms with respect to the distribution of anatomic location of lymph nodes for each identification method. We will also use Fisher's exact test to compare identification methods with respect to the distribution of anatomic location of lymph nodes. We summarize these data using both the PP and mITT analysis sets.

Identification Method	B-P Arm		P-B Arm		Total	
	N	%	N	%	N	%
PINPOINT						
Left obturator/internal iliac						
Left external iliac						
Left common iliac						
Right obturator/internal iliac						
Right external iliac						
Right common iliac						
Presacral						
Para-aortic node below IMA						
Para-aortic node above IMA						
Other						
Blue Dye						
Left obturator/internal iliac						
Left external iliac						
Left common iliac						
Right obturator/internal iliac						
Right external iliac						
Right common iliac						
Presacral						
Para-aortic node below IMA						
Para-aortic node above IMA						
Other						
Following a Channel (No Dye Present in Node)						
Left obturator/internal iliac						
Left external iliac						
Left common iliac						
Right obturator/internal iliac						
Right external iliac						
Right common iliac						
Presacral						
Para-aortic node below IMA						
Para-aortic node above IMA						
Other						
Appearance (No Dye Present in Node)						
Left obturator/internal iliac						
Left external iliac						
Left common iliac						
Right obturator/internal iliac						
Right external iliac						
Right common iliac						
Presacral						
Para-aortic node below IMA						
Para-aortic node above IMA						
Other						

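### The SAP compares the arms on node location with Fisher's exact test on nodes, although subjects are randomised, so p-values in the large PINPOINT and Blue dye blocks can be too small

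*SAP*

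**What the plan says.** In the SAP, Secondary Efficacy Outcomes, the text introducing Table 8 plans Fisher's exact test to "compare study arms with respect to the distribution of anatomic location of lymph nodes for each identification method". Table 8 has ten locations in each of four blocks: PINPOINT, Blue dye, nodes found by following a channel, and nodes found by appearance. The last two blocks hold nodes without dye. No adjustment for nodes from the same subject is stated. Protocol 10.6 asks only for a tabulation of anatomic distribution, so the test is an addition made in the SAP.

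Randomisation is by subject and stratified by site (Protocol 5.1): "Subjects will be randomly assigned on a one to one (1:1) basis". Protocol 10.4 expects 3 to 4 nodes per subject and 525 nodes from about 150 subjects.

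Elsewhere the plan allows for the nesting. Of the sample size, Protocol 10.4 says "The power calculation was performed for a 2-level hierarchical model in which nodes are nested within subject", and it applies a variance inflation factor. The primary outcome uses a clustered matched-pair method, and the duct outcome uses a similar interval.

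**The concern.** Fisher's exact test takes its p-value from a distribution in which every counted unit is allocated to an arm separately. Here about 150 allocations produce about 441 PINPOINT nodes (0.84 × 525). Nodes from one subject share that subject's drainage anatomy and one operation, so their locations may be correlated. If they are, the arm-by-location table varies more by chance than Fisher's test assumes, and the p-value is too small.

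This is the only efficacy comparison in the SAP that sets one arm against the other. A small p-value could be taken to mean that mapping order changes where a method finds nodes. The test is repeated for each identification method, and the data are summarised in both the PP and mITT sets. The point concerns the between-arm comparison only, not the comparison of identification methods planned alongside it.

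**Working it through.** **The plan's own figure.** Protocol 10.4: VIF = 1 + (2 × 3.5 − 1) × 0.125 = 1.75, and ESS = 525 / 1.75 = 300. With rates of 84% and 80% and a 5-point margin, power = Φ(0.09 / √[(0.80 × 0.20 + 0.84 × 0.16) / 300] − 1.96) = Φ(0.09 / 0.0313 − 1.96) = 81.9%, against 82% stated. It reproduces. The documents give no operating figure for the Table 8 test.

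**Inputs from the documents.** 150 subjects, taken as 75 per arm; 3.5 nodes per subject, so 0.84 × 3.5 = 2.94 PINPOINT nodes per subject; ICC 0.07 (estimate) and 0.125 (maximum), from Protocol 10.4; bilateral mapping with ICG of 65% and 79%, and with blue dye of 43%, from the prior studies in Protocol 1.1.4.

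**Assumptions.** The ICC for location is borrowed from detection, and the shares of nodes at each location are assumed.

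**Rough ceiling.** For a node-level comparison between arms, the design effect is 1 + (3.5 − 1) × ICC, which is 1.175 at 0.07 and 1.3125 at 0.125. Dividing the 5% critical value of chi-square with 9 df by these gives false-positive rates of 10.9% and 16.8%. Simulation with equal clustering over all ten locations gives 11.3% and 17.7%. This ignores that both sides of the pelvis are mapped in each subject, which spreads a subject's nodes over left and right.

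**Simulation with left/right structure, no true arm difference, nominal 5%.**

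- Model A: 1 + Poisson(1.94) nodes per subject, seven regions with subject-specific (Dirichlet) probabilities, and the three lateral regions (0.34 + 0.40 + 0.12 = 0.86 of nodes) split by side to give ten locations. Side is either random or alternating.
- Model B: 3 or 4 nodes per subject, each seen by the method with probability 0.84 (0.80 for Blue dye), six lateral locations. The bilateral share is fixed among subjects with at least two such nodes, and all other subjects map on one side only. The ICC applies to nodal station; side adds its own clustering.

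With random side in Model A and ICC 0, the bilateral share is 1 − 2 × 0.57 × exp(−1.94 × 0.43) + 0.14 × exp(−1.94 × 0.86) = 1 − 0.495 + 0.026 = 53%. With alternating side it is about 73%.

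| Model | Bilateral | ICC 0 | ICC 0.07 | ICC 0.125 |
|---|---|---|---|---|
| A, side random (4,000 trials) | about 53% | 5.0% | 8.4% | 12.7% |
| A, side random, repeat (1,000) | about 53% | 3–4% | 7.7% | 10.8% |
| A, alternating (4,000) | about 73% | 3.8% | 5.9% | 9.0% |
| A, alternating, repeat (1,000) | about 73% | 3–4% | 5.8% | 7.4% |
| B (1,000) | 65% | 6.5% | 8.4% | 8.6% |
| B (1,000) | 79% | 4.8% | 4.8% | 6.2% |
| B (1,000) | 90% | 2.8% | 4.6% | 5.4% |
| B (1,000) | 100% | 3.4% | 3.4% | 4.5% |
| B, Blue dye (1,000) | 43% | 9.1% | 11.8% | 14.1% |

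Monte Carlo standard error is √[p(1 − p)/n]: about 0.7 points at 5% with 1,000 trials, and 0.45 points at 9% with 4,000.

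**Small blocks.** A dye-free block of about 40 nodes (an assumed size), with about one node per contributing subject, gives 3% to 6% at every ICC from 0 to 0.125.

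**Subject-level permutation.** Reassigning whole subjects to arms gives about 4% to 6% in every scenario. These runs had no sites, so the within-site version was not itself simulated.

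**The case against.** Four objections carry weight.

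- **The ICC is borrowed.** "We expect the ICC to be at most 0.125 based on our estimate of the ICC = 0.07" refers to detecting a node, not to where it lies. A reader might infer that the 5% level fails at the plan's own maximum ICC. The documents do not support that, because they give no ICC for location.
- **The larger figures need little bilateral mapping.** A reader might take the 11% to 18% from the plain design effect, or the 13% from random side, as the expected size. The ICG bilateral rates in Protocol 1.1.4 (65% and 79%) are above the 53% that random side implies, and Protocol 8.3.1 has both sides mapped. These favour the lower end, and at 79% with ICC 0.07 one model shows no inflation.
- **Not every block is affected.** A reader might infer that all between-arm p-values in Table 8 are too small. The dye-free blocks may hold few nodes, and no inflation is shown there.
- **The unit is inferred.** Table 8's caption is not in the available text, and Table 6 counts subjects although its endpoint is nodes. The node is still the natural reading: a subject with nodes in several locations would fall in several rows, and Fisher's test needs exclusive categories.

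It is also fair that nothing decisive hangs on this test. The stated objective is to describe the distribution, and no level or decision rule is given for these p-values. The SAP does not say whether they enter the step-down procedure for the secondary objectives.

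These objections limit the size and importance of the point. They do not remove the mismatch between a test that allocates nodes and a trial that allocates subjects.

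**Conclusion.** The point holds, at low severity. On the natural reading that nodes are counted, the between-arm Fisher test uses the wrong unit of allocation and departs from the plan's handling of nesting elsewhere.

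In the PINPOINT block the false-positive rate is roughly 6% to 9% at bilateral mapping near the quoted ICG rates, and up to about 13% if side is random within subject. It is near or below 5% if the correlation of location within subject is about zero, or if nearly all subjects map on both sides. The Blue dye block could be more affected if its bilateral rate is as low as the quoted 43% (about 12% to 14% in one model). All these figures rest on borrowed ICCs and assumed location shares.

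The primary non-inferiority and superiority results are unaffected, because they use a method for clustered pairs.

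**What to change.** In the SAP, replace the sentence on the between-arm comparison in Table 8 with one of the following.

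1. Keep the arm-by-location table and a chi-square-type statistic for each identification method. Obtain the p-value by permuting the B-P/P-B label across whole subjects within site, keeping each subject's nodes together. Fix the seed and the number of draws in advance. This follows the site-stratified randomisation and needs no assumed ICC.
2. Present Table 8 without between-arm p-values, which matches the tabulation in Protocol 10.6.

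In either case, state that Table 8 counts nodes. If p-values are kept, also state whether they enter the step-down procedure.

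The cost is one SAP sentence and, for the first option, a few lines of code. No data or subjects are added. With the first option, p-values will usually be somewhat larger.

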#### 8.3.1.5 Classification of Lymph Nodes

All LNs identified will be classified as:

[figure not shown]
1. Fluorescent only
2. Blue only
3. Both (Fluorescent and blue)
4. Abnormal or palpably hard
5. Non-stained node found at termination of fluorescent duct
6. Non-stained node found at termination of blue duct
7. Non-stained node found at termination of fluorescent and blue duct

All LN identified and subsequently removed will be histologically examined to confirm the presence of lymphoid tissue according to [section 8.5](#).

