$$\begin{aligned} H_{05}: d_t &\leq d_c - 0.05 \\ H_{15}: d_t &> d_c - 0.05 \end{aligned}$$

To test this hypothesis we will estimate the difference  $d_t - d_c$  with a 95% two-sided confidence interval. We will estimate this confidence interval in a manner similar to that described for the primary outcome. We will perform this analysis using the PP analysis set to test the inferiority hypothesis ( $H_{05}$ ) stated above, and if the lower bound of the interval is greater than -0.05 we will claim non-inferiority. If and only if we reject the inferiority hypothesis ( $H_{05}$ ) we will use the mITT analysis set to test for superiority, and if the lower bound of the interval is greater than 0 we will claim superiority.

We will also tabulate the anatomic distribution of LNs identified by each dye.

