Adenosquamous Carcinoma						
Neuroendocrine						
Clear Cell Carcinoma						
Undifferentiated						
Mixed						
Surgical Procedure						
Hysterectomy						
Radical Hysterectomy						
Radical Trachelectomy						
Bilateral Salpingo-Oophorectomy						
Unilateral Salpingo-Oophorectomy						
Ovarian Transposition						
Sentinel Node Mapping						
Pelvic Node Sampling						
Pelvic Node Dissection						
Para-Aortic Node Sampling						
Para-Aortic Node Dissection						
Other						
Length of Surgery (minutes)						
Median (Min – Max)						
Dose of IC2000 (mg)						
Median (Min – Max)						
Dose of Blue Dye (mg)						
Median (Min – Max)						

Primary Efficacy Outcome

The primary objective of this study is to assess the effectiveness of intraoperative PINPOINT Near Infrared Fluorescence Imaging (PINPOINT) in identification of LNs in subjects with uterine and cervical malignancies who are undergoing LN mapping. Table 3 summarizes the study primary outcome.

Table 3. Lymph Nodes Identified						
Identification Method	B-P Arm		P-B Arm		Total	
	N	%	N	%	N	%
PINPOINT Only						
Confirmed as NOT Lymphatic Tissue						
Confirmed as Lymphatic Tissue						
Confirmed as Lymphatic Tissue (negative for cancer)						
Confirmed as Lymphatic Tissue (positive for cancer)						
Blue Dye Only						
Confirmed as NOT Lymphatic Tissue						
Confirmed as Lymphatic Tissue						
Confirmed as Lymphatic Tissue (negative for cancer)						
Confirmed as Lymphatic Tissue (positive for cancer)						
Both PINPOINT and Blue Dye						
Confirmed as NOT Lymphatic Tissue						
Confirmed as Lymphatic Tissue						
Confirmed as Lymphatic Tissue (negative for cancer)						
Confirmed as Lymphatic Tissue (positive for cancer)						
Following a Fluorescent Duct (No Dye Present in Node)						
Confirmed as NOT Lymphatic Tissue						
Confirmed as Lymphatic Tissue						
Confirmed as Lymphatic Tissue (negative for cancer)						
Confirmed as Lymphatic Tissue (positive for cancer)						
Following a Fluorescent Duct (Blue Dye Present in Node)						
Confirmed as NOT Lymphatic Tissue						
Confirmed as Lymphatic Tissue						
Confirmed as Lymphatic Tissue (negative for cancer)						
Confirmed as Lymphatic Tissue (positive for cancer)						
Following a Blue Duct (No Dye Present in Node)						
Confirmed as NOT Lymphatic Tissue						
Confirmed as Lymphatic Tissue						
Confirmed as Lymphatic Tissue (negative for cancer)						
Confirmed as Lymphatic Tissue (positive for cancer)						

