Following a Blue Duct (Fluorescent Dye Present in Node)						
Confirmed as NOT Lymphatic Tissue						
Confirmed as Lymphatic Tissue						
Confirmed as Lymphatic Tissue (negative for cancer)						
Confirmed as Lymphatic Tissue (positive for cancer)						
Following a Blue and Fluorescent Duct (No Dye Present in Node)						
Confirmed as NOT Lymphatic Tissue						
Confirmed as Lymphatic Tissue						
Confirmed as Lymphatic Tissue (negative for cancer)						
Confirmed as Lymphatic Tissue (positive for cancer)						

Table 3. Lymph Nodes Identified

Identification Method	B-P Arm		P-B Arm		Total	
	N	%	N	%	N	%
Appearance (No Dye Present in Node)						
Confirmed as NOT Lymphatic Tissue						
Confirmed as Lymphatic Tissue						
Confirmed as Lymphatic Tissue (negative for cancer)						
Confirmed as Lymphatic Tissue (positive for cancer)						
Total						
PINPOINT						
Confirmed as NOT Lymphatic Tissue						
Confirmed as Lymphatic Tissue						
Blue Dye						
Confirmed as NOT Lymphatic Tissue						
Confirmed as Lymphatic Tissue						
Neither Dye						
Confirmed as NOT Lymphatic Tissue						
Confirmed as Lymphatic Tissue						
Total						

To assess the effectiveness of PINPOINT in the identification of LNs, a non-inferiority test will be performed using the per-protocol (PP) analysis set.

$$H_{01}: p_t \leq p_c - 0.05$$

$$H_{11}: p_t > p_c - 0.05$$

Here p_t and p_c represent the effectiveness of LN mapping with PINPOINT and Blue dye respectively. We define the numerator for p_t as the number of nodes identified with PINPOINT (i.e., with PINPOINT alone or with both Blue dye and PINPOINT) and confirmed as lymphoid tissue, and we define the numerator for p_c as the number of nodes identified with Blue dye (i.e., with Blue dye alone or with both Blue dye and PINPOINT) and confirmed as lymphoid tissue. We define the denominator for both p_t and p_c as the number of nodes identified by ANY method (i.e., PINPOINT alone, Blue dye alone, both Blue dye and PINPOINT, abnormal appearance or palpably hard, non-stained node found at termination of Fluorescent duct, non-stained node found at termination of Blue duct, non-stained node found at termination of duct stained with both Blue dye and Fluorescent dye). The denominator will include excised nodes confirmed as lymphoid tissue.

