The first secondary outcome is the ability of PINPOINT and Blue dye to detect at least one lymph node in a subject. Let q_t and q_c represent the proportion of subjects with a least one node identified and confirmed as lymphoid tissue with PINPOINT and Blue dye respectively, divided by the total number of subjects where mapping was attempted. That is, the numerator for q_t is the number of subjects with at least 1 node identified with PINPOINT (PINPOINT alone, both Blue dye and PINPOINT, non-stained node found at termination of Fluorescent duct, Blue-stained node found at termination of a Fluorescent duct, non-stained node found at termination of duct stained with both Blue dye and Fluorescent dye) and confirmed as lymphoid tissue, and the numerator for q_c is the number of subjects with at least 1 node identified with Blue dye (Blue dye alone, both Blue dye and PINPOINT, non-stained node found at termination of Blue duct, Fluorescent-stained node found at termination of Blue duct, non-stained node found at termination of duct stained with both Blue dye and Fluorescent dye) and confirmed as lymphoid tissue. The denominator of both q_t and q_c is the number of subjects where mapping was attempted.

Table 4 summarizes the data to address this secondary objective.

Table 4. Number of Subjects with ≥ 1 Lymph Node Identified						
Identification Method	B-P Arm		P-B Arm		Total	
	N	%	N	%	N	%
PINPOINT						
Blue Dye						
Number of Subjects						

We will test the following hypotheses:

$$H_{03}: q_t \leq q_c - 0.05$$

$$H_{13}: q_t > q_c - 0.05$$

To test this hypothesis we will estimate the difference $q_t - q_c$ with a 95% two-sided confidence interval. We will perform this analysis using the PP analysis set to test the inferiority hypothesis (H_{03}) stated above, and if the lower bound of the interval is > -0.05 we will claim non-inferiority. If and only if we reject the inferiority hypothesis (H_{03}) we will use the mITT analysis set to test for superiority, and if the lower bound of the interval is > 0 we will claim superiority.

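### SAP Table 8 does not say where nodes found with both dyes are counted, and Fisher's exact test between identification methods does not suit them on either reading

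*SAP*

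**What the plan says.** Under Secondary Efficacy Outcomes, the SAP sets out Table 8 with four blocks: PINPOINT, Blue Dye, undyed nodes reached by following a channel, and undyed nodes taken for their appearance. Each block lists ten locations. Two tests are planned on these node counts. One is Fisher's "exact test to compare identification methods with respect to the distribution of anatomic location of lymph nodes". The other is Fisher's "exact test to compare study arms with respect to the distribution of anatomic location of lymph nodes for each identification method".

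Table 3 of the SAP gives dual-identified nodes their own rows ("Both PINPOINT and Blue Dye"), beside rows for each dye alone. Protocol 8.3.1.5 likewise makes them a separate class, class 3. Table 8 has no such block and no sentence on where they go.

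Elsewhere the SAP counts dual nodes under each dye. The primary numerator for PINPOINT covers nodes found "with PINPOINT alone or with both Blue dye and PINPOINT", and the Table 4 outcome counts subjects "with at least 1 node identified with PINPOINT (PINPOINT alone, both Blue dye and PINPOINT". Blue dye is handled the same way, and Table 5 follows Table 4.

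Protocol 10.6 plans no test on location: "We will also tabulate the anatomic distribution of LNs identified by each dye".

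In Safety Outcomes, Table 9 has columns that count adverse events by arm. Fisher's test is planned there on intensity and relationship for each event term.

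**The concern.** Fisher's exact test conditions on the margins of a table in which every unit falls in exactly one cell and units are independent. A node entered in both dye blocks breaks the first condition. It contributes the same location to both sides, so the two distributions are pulled together and the test becomes conservative. Nodes nested in subjects break the second condition. The SAP handles both features for the primary outcome, with a clustered matched-pair method, but does not carry them over to Table 8.

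Anatomic distribution is a listed secondary objective, and the secondary outcomes are meant to support labelling. A large p-value could be taken to mean that the two dyes map the same sites when the test had little chance of showing a moderate difference.

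**Working it through.** **Inputs.** Protocol 10.4 gives 84% detection for ICG, 80% for Blue dye, 525 nodes, 3.5 nodes per subject, 150 subjects, an ICC of at most 0.125, and a published range of "40-80% for Blue dye". I take the rates as shares of stained nodes, as the SAP's primary definition does.

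**The plan's own figure.** VIF = 1 + (2 × 3.5 − 1) × 0.125 = 1.75. ESS = 525 / 1.75 = 300. Power = Φ(0.09 / √((0.80 × 0.20 + 0.84 × 0.16) / 300) − 1.96) = 81.9%, against the stated 82%. This concerns the primary test only; the documents state no operating characteristic for Table 8.

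**Shared nodes if dual nodes are entered twice.** PINPOINT 0.84 × 525 = 441; Blue dye 0.80 × 525 = 420. Minimum overlap is 441 + 420 − 525 = 336 (64%). With independent detection it is 0.84 × 0.80 × 525 = 352.8 (67%).

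**Variance ratio.** For a location with share π, the test takes the variance of the difference in shares as π(1−π)(1/n_P + 1/n_B). The shared nodes add a covariance, so under the null the true variance is π(1−π)(1/n_P + 1/n_B − 2n_both/(n_P n_B)). Assumed over true is (n_P + n_B) / (n_P + n_B − 2n_both), whatever the location mix:

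- 336 shared: 861 / (861 − 672) = 4.56
- 352.8 shared: 861 / (861 − 705.6) = 5.54
- 84%/40%: 441 + 210 − 525 = 126 shared; 651 / (651 − 252) = 1.63

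**Rejection rates.** By the chi-square approximation (9 df, critical value 16.92), the size at 336 shared is P(χ²₉ > 16.92 × 4.56), about 6 × 10⁻¹³. Power was simulated with Monte Carlo Fisher tests (2,000 data sets, independent nodes). The location mix is assumed: per side 18% obturator/internal iliac, 25% external iliac and 3% common iliac, with 2% in each of the four other cells. PINPOINT-only nodes are shifted toward obturator/internal iliac.

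| Shift (assumed) | All nodes, 336 shared | All nodes, 353 shared | Single-dye nodes only (105 v 84) |
|---|---|---|---|
| none | 0.0% | 0.0% | 4.5% |
| 20 points | 0.0% | 0.0% | 51.5% |
| 30 points | 0.0% | 0.0% | 91.1% |
| 40 points | 0.85% | 0.0% | 99.8% |
| 60 points | 80.4% | 11.5% | 100% |
| opposite 30-point shifts | 63.9% | 3.3% | 100% |

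At 84%/40% with 126 shared, null rejection is 0.25%. Power at 20 points is 53.2%, against 72.1% on single-dye nodes.

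**Clustering.** Applying the plan's VIF of 1.75 to location (an assumption) leaves true over assumed variance at 1.75 / 4.56 = 0.38 with 336 shared, and the size still near zero. At 84%/40% it gives 1.75 / 1.63 = 1.07, a size of about 7%. The strong conservatism therefore depends on high overlap.

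**Single-dye reading.** Size is 4.5% in the table above, ignoring clustering. At least 336 of 525 nodes then have no block. At 84%/40% the minimum left out is 126 of 525 (24%), no longer a majority.

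**All four blocks in one test.** Simulated null rejection was 0.2% with 17 undyed nodes and about 2% with some 6% of nodes undyed (both assumed). The overlap remains, and a rejection could come from the undyed nodes alone.

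**Between-arm location test.** Nodes are nested in randomised subjects, and the documents give no ICC for location; the 0.125 concerns detection. With an assumed location ICC of 0 to 0.125, simulated size was 3.8% to 13.1% when nodes alternate sides and 5.4% to 16.8% when they do not. This only illustrates that the error can go either way.

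**Table 9 Fisher test.** Event counts are independent units only if no subject has the same term twice. With 3 to 30 affected subjects per arm, simulated size was 0% to 2.6% with no repeats and 8.5% to 11.0% if half of them repeat (assumed rates).

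**The case against.** The strongest reply is that double entry is nowhere written for Table 8. The labels there do differ from Tables 4 and 5: those outcomes count undyed nodes at the end of a duct under the dye, whereas Table 8 gives such nodes their own block. This stands, and double entry is an inference, supported mainly by the primary definition. It does not rescue the plan, because the single-dye reading leaves the dual nodes with no place.

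The SAP also says identification methods, not PINPOINT against Blue dye. That stands too; the four-block version is covered above and has the same overlap.

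A reader might infer that a non-significant result is simply uninformative. The figures do not support that. With 336 shared nodes the test has 80% power for a 60-point shift, and at 84%/40% it has 53% for 20 points. The limit applies to moderate differences under high overlap.

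A reader might also infer that the exact binomial incidence interval in Safety Outcomes counts events over subjects. The SAP does not say so. An exact binomial interval points to subjects, and Protocol 10.6.2 plans the number and percentage of subjects with events. No fault is claimed there.

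Finally, neither document says that a large p-value will be read as similar mapping, and no hypothesis or margin attaches to this objective. That is why the point is minor.

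**Conclusion.** The planned between-method test needs correcting on either reading. If dual nodes are counted twice, it overstates the variance about 4.6-fold or more at the planned rates, has a null rejection rate near 0%, and cannot support similarity for moderate location differences. If they are left out, it roughly keeps its size, apart from clustering, but omits at least 64% of nodes at those rates. Clustering is ignored in both cases.

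The overlap and variance ratios follow from the plan's rates alone. The power figures rest on an assumed location mix and assumed shifts. Confidence is high in the arithmetic and moderate that double entry is intended.

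The between-arm location test has an error of unknown size and direction. The Table 9 test is affected only if subjects repeat a term. Severity is minor: no success rule and no primary analysis depends on any of these tests.

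**What to change.** **Table 8, methods.** Add a block for nodes found with both dyes and state how they are counted. Drop the between-method p-value, which returns to the protocol's plan to tabulate. If a test is wanted, compare PINPOINT and Blue dye location shares over all nodes, paired, with a subject-clustered covariance. Merge sparse sites for the test only, drop one category, and keep the full ten-location table. With four categories and 353 shared nodes, this test had simulated size 5.1% to 6.1% and about 63% power at 20 points (same assumed mix, location ICC 0 to 0.125). Leave the undyed blocks descriptive.

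**Table 8, arms.** Permute arm labels by subject within site, matching the site-stratified randomisation in Protocol 5.1, or drop the p-value.

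**Table 9.** For the Fisher test, count each subject once per term, at maximum intensity and strongest relationship. Keep event counts as description.

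**Cost.** SAP wording, one extra table block and a few lines of code; no new data. The descriptive option gives up the between-method p-value. The primary analysis is untouched.
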